## SYNOPSIS

Study title:	A Phase 1/2 Study to evaluate the Safety, Pharmacokinetics, and Anti-Tumour Activity of the Myc Inhibitor OMO-103 administered intravenously in Patients with Advanced Solid Tumours
Protocol number:	OMO-103-01
Type of study:	Phase 1/2
Sponsor:	Peptomyc S.L.
Coordinating Investigator:	[name] Oncology Department Vall d'Hebron University Hospital (VHIO) [name] Spain e-mail: [contact]
Study drug:	OMO-103
Dose to be studied:	Part 1: Dose Escalation: 5 OMO-103 dose levels planned, including 0.48 mg/kg, 1.44 mg/kg, 2.88 mg/kg, 4.32 mg/kg and 6.48 mg/kg. Part 2: Dose Expansion: OMO-103 at the RP2D found in the previous part of the study.
Dosage form:	OMO-103 solution for infusion presented in vials.
Route:	In both study parts, OMO-103 will be administered IV as a 30-45 min infusion once weekly.
Study centres:	Planned: Up to 15 centres in up to 5 countries
Study objectives:	Primary (Part 1: Dose Escalation): 

To evaluate the safety and tolerability of OMO-103 in adult patients with advanced solid tumours.

 Secondary (Part 1: Dose Escalation): 

To establish and confirm the RP2D and dosing regimen of OMO-103 for further development.

To characterise the PK of OMO-103.

To evaluate preliminary anti-tumour activity in the dose escalation part.

To assess the development of human ADA to OMO-103.

 Primary (Part 2: Dose Expansion): 

To assess the preliminary anti-tumour activity of OMO-103 monotherapy as measured by ORR according to standard criteria (RECIST v1.1 [Eisenhauer 2009]).

	
Secondary (Part 2: Dose Expansion):
 
 
• To confirm the RP2D and dosing regimen of OMO-103 for further development.
 
• To assess the type, incidence, severity, timing, seriousness, and relatedness of AEs and laboratory abnormalities.
 
• To characterise the PK of OMO-103.
 
• To assess other efficacy parameters in patients with advanced solid tumours including DCR, PFS, OS, TTP, TTR and DOR by RECIST v1.1.
 
• To assess the development of human ADA to OMO-103.
 
 
Exploratory (Both Parts 1 and 2):
 
 
• Evaluation of biomarkers.
 
• Myc expression levels.
 

Study design:	
This study is an open label, two-part, FIH Phase 1/2 dose-finding study designed to determine the safety, tolerability, PK, PD and proof-of-concept of OMO-103 in patients with advanced solid tumours.
 
The study consists of two parts:
 
 
• Part 1: Dose escalation in patients with advanced solid tumours, including 5 OMO-103 dose levels. Approximately 11 to 24 patients in total will be enrolled in Part 1, covering 5 dose levels with the primary objective of determining the safety and tolerability of OMO-103 and defining an appropriate dose for further evaluation in Part 2. The study will start with an accelerated-titration dose-escalation scheme enrolling one evaluable patient per cohort for the first 2 dose levels followed by a classic 3+3 design.
 
• Part 2: Dose expansion where at least 3 parallel groups of patients with advanced NSCLC, TNBC and CRC will be treated at the RP2D of OMO-103 to further characterise the safety, tolerability, PK, PD and anti-tumour activity of OMO-103. Approximately 18 patients will be enrolled in each of the 3 parallel groups of patients (NSCLC, TNBC, CRC) in Part 2. Note: If an objective response is observed in a tumour group within Part 1, or a long period without disease progression is observed (in Part 1), additional tumour groups may be added in this Phase 1/2 study for further assessment.
 

Diagnosis and main criteria for inclusion:	
Male or female patients, 18 years of age or older who sign the informed consent document, are willing and able to comply with the study protocol and have:

**Part 1 (Dose Escalation):**

Histologically or cytologically proven advanced solid tumour for which there is no curative therapy and has progressed on SOC treatment or is intolerant to or has no available SOC or SOC unacceptable.

**Part 2 (Dose Expansion):**

Histologically or cytologically proven advanced NSCLC whose tumours are KRAS-mutated and where the disease has progressed after a chemotherapy and immunotherapy regimen (at least two prior lines of standard therapy), advanced TNBC where the disease has progressed after having received at least one line of prior systemic treatment for advanced disease and advanced CRC whose tumours are RAS mutated and where the disease has progressed after at least two prior lines of standard therapy.

**Parts 1 and 2:**

- Patient must have measurable disease as per RECIST v1.1 criteria and documented by CT and/or MRI. NOTE: Lesions to be used as measurable disease for the purpose of response assessment must either:
  - a. not reside in a field that has been subjected to prior radiotherapy, or
  - b. have demonstrated clear evidence of radiographic progression since the completion of prior radiotherapy and prior to study enrolment.
- Tumour biopsy (either from the primary tumour or from metastases) during Screening and during Treatment should be obtained from the patients. Discussion needed with Sponsor if considered not feasible. In Part 1, biopsy obtained only from the 3rd dose level onwards.

Note: In case a patient has had a tumour biopsy in the previous 6 months and a paraffin block is available, a new biopsy does not need to be done at Screening.

- For each patient undergoing pre- and on-treatment biopsies, the identified lesion to be biopsied should not have been previously irradiated and should not be the only lesion being utilised as a measurable-disease target lesion for objective response assessment. Patients must have tumour lesions that can be accessed for biopsy with acceptable clinical risk in the judgement of the Investigator.
- Documented progression on or following the last line of therapy.
- ECOG performance status up to 1.

- Life expectancy of  $\geq 12$  weeks.
- Resolution of all acute, reversible toxic effects of prior therapy or surgical procedure to Grade  $\leq 1$  (except alopecia and peripheral neuropathy to Grade  $\leq 2$ ).
- Adequate organ function as defined by the following criteria:

Haematological:

- a. Neutrophils  $\geq 1,000/\mu\text{L}$
- b. Platelets  $\geq 100,000/\mu\text{L}$
- c. Haemoglobin  $\geq 9$  g/dL

Renal:

- a. Creatinine Clearance (calculated via Cockcroft-Gault Equation)  $\geq 40$  mL/min

Hepatic:

- a. Serum total bilirubin  $\leq 1.5$  ULN or
- b. Direct bilirubin  $\leq$  ULN for patients with total bilirubin  $> 1.5$  ULN
- c. AST/ SGOT and ALT/ SGPT  $\leq 2.5$  ULN or  $\leq 5$  ULN if liver metastases

Coagulation:

- a. INR  $\leq 1.5$
- b. aPTT  $\leq 1.5$  ULN

Chemistry:

- a. Albumin  $> 25$  g/L

- If not postmenopausal or surgically sterile, female patients must be willing to practice at least one highly effective methods of birth control (defined as having a low failure rate) for at least a menstrual cycle before and for 4 months after last study drug administration.
- Male patients and their sexual partners must use an appropriate contraceptive from Screening for 4 months after last study drug administration.

**Total sample size:** In total, about 78 eligible patients will be enrolled.

**Number of planned visits:** Part 1: Dose Escalation

- **Screening period:** 28 days to 1 day prior 1st dose
- **Treatment period:**
  - Cycle 1 (DLT period): C1D1, C1D2, C1D3, C1D4, C1D5, (Days 3 to 5 only from dose level 3 onwards for PK evaluation), C1D8, C1D15, C1D16 or C1D17 (Day 16 or Day 17 for biopsy and only from dose level 3 onwards)
  - Cycle 2: C2D1, C2D8, C2D15

	
 
- Cycle 3*: C3D1, C3D2, C3D3, C3D4, C3D5, (Days 3 to 5 only from dose level 3 onwards for PK evaluation), C3D8, C3D15
 
 
*NOTE: Assumed 3 cycles but these are unlimited. The planned visits of other cycles will occur on D1, D8 and D15, except for every 3 cycles from Cycle 3 (i.e., Cycle 6, Cycle 9, etc. as PD biomarkers for target validation will be sampled on D1, as well as on D2 during these cycles).
 
 
- EOT visit
 
• Follow-up period: 1-Month Follow-up visit
 

	
Part 2: Dose Expansion
 
 
• Screening period: 28 days to 1 day prior 1st dose
 
• Treatment period: 
 
- Cycle 1: C1D1, C1D2, C1D8, C1D15
 
- Cycle 2: C2D1, C2D8, C2D15, C2D16 or C2D17 (Day 16 or Day 17 for biopsy)
 
- Cycle 3: C3D1, C3D2, C3D8, C3D15,
 
- Cycle 4: C4D1, C4D8, C4D15,
 
- Cycle 5: C5D1, C5D8, C5D15,
 
- Cycle 6*: C6D1, C6D2, C6D8, C6D15,
 
 
*NOTE: Assumed 6 cycles but these are unlimited. The planned visits of all other cycles will occur on D1, D8 and D15, except for every 3 cycles from Cycle 3 (i.e., Cycle 6, Cycle 9, etc. as PD biomarkers for target validation will be sampled on D1, as well as on D2 during these cycles).
 
 
- EOT visit
 
• Follow-up period: 6-Month Follow-up period, including monthly visits if feasible. Telephone visits may be allowed if considered appropriate, e.g., hospice patients
 
 
 

Safety parameters:	Physical examinations; vital signs assessments; ECOG performance status; laboratory analyses; autoimmunity; 12-Lead ECG; reported AEs.
Efficacy parameters:	
Tumour response:
 
 
• ORR (primary efficacy endpoint);
 
• DCR; PFS; OS; TTP; TTR; DOR (secondary efficacy endpoints) (only Part 2).
 

Pharmacokinetic parameters:	PK parameters of OMO-103: AUC; C min ; C max ; t max ; t 1/2 .
PD parameters:	Circulating human ADA to OMO-103; Ki67 and CC3 by IHC; Immune infiltration by IHC (CD3, CD4/CD8, PD-1/ PD-L1) and others to be determined; Multiplex assay from biopsies (e.g., MYC-

expression levels); Cytokines and other PD biomarkers for the purpose of an optional genetic analysis and for target validation; PBMC and immune characterisation blood samples only during Part 2 (Dose Expansion).

**Statistical methods:**Sample Size

The sample size is determined based on clinical rather than statistical considerations. For the dose escalation part, up to 24 patients are anticipated to be recruited. The number of patients in this study is consistent with Phase 1 dose finding studies. In Part 2, at least 3 parallel groups of patients with advanced NSCLC, TNBC and CRC will be treated. Approximately 18 patients will be enrolled in each group in Part 2.

General Considerations

In general, all data will be summarised using appropriate descriptive statistics by per dose cohort and for the expansion groups where applicable. Summary tabulations will be presented that display the number of patients (N), number of observations, mean, SD, median, minimum, and maximum for continuous variables, and the number and percent (of non-missing values) per category for categorical data by absolute and relative frequencies.

Unless indicated otherwise, summary statistics will be reported for observed data only. Missing data will not be imputed. If a baseline value is missing, no change from baseline will be calculated.

Baseline is defined as the last assessment before the start of IMP administration.

Safety data will be reviewed continuously and integrated with PK and PD data at the end of dose escalation in order to determine the dose to be administered during the dose expansion part of the study. The same data will be integrated at the conclusion of the study in order to determine the RP2D to be used in future trials of OMO-103.

Interim Analysis

An interim analysis is planned at the end of Part 1 (Dose Escalation) to provide an overview of available study results at that stage. Note: This interim analysis will not replace the role of the SMC and will not affect dose escalation rules, nor the decision to proceed to Part 2 (Dose Expansion).

Another interim analysis is planned in the dose expansion part. After half of the patients in all groups (i.e., 9 patients per group) have been included and treated for 3 cycles, efficacy and safety will be analysed. If no response (as per RECIST v1.1) is seen during the interim analysis in at least one patient regardless of group, or for safety reasons, recruitment could be stopped (or the dose reduced) following discussion between the Investigator, the SMC and the Sponsor.

If there are no safety concerns and a response is seen, the study will continue until 18 patients have been recruited in each group.

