3.3.2 Study Flow Chart Part 2: Dose Expansion

Protocol Activities (Window, Days)	Screening	Treatment period							End of treatment ±3 days [1]	6-month follow-up (monthly visits ±3 days) [2]
		Cycle I				Cycle 2+ (unlimited)				
		28 days to 1 day prior 1 st dose	Day 1 ±1 day	Day 2	Day 8 ±1 day	Day 15 ±1 day [14]	Day 1 ±1 day	Day 8 ±1 day		
Baseline Documentation										
Informed Consent	X									
Eligibility Assessment	X									
Medical/Oncological History [3]	X									
Physical Examination [4]	X	X	X	X	X	X	X	X	X	X
ECOG Performance Status	X	X				X			X	X
12-Lead ECGs [7]	X	X				X			X	
Laboratory Studies										
Safety Blood Sampling [5]	X	X	X	X	X	X	X	X	X	X
Urinalysis [5]	X	X	X	X	X	X	X	X	X	X
PK Assessment [6]		X	X			X				
ADAs	X			X (Pre-dose)	X (Pre-dose)	X (Pre-dose)			X	X [16]

Study Flow Chart Part 2: Dose Expansion (continued)

Autoimmunity [12]	X					X			X	
Efficacy/PD Assessments										
CT/MRI [8]	X							C3 [8]	X	
Tumour Biopsy [9]	X							C2 D16 or D17 [9]	X (optional)	
PD markers [10]	X	X	X			X		C2 D16 or D17 [10]	X	X
PBMC blood PD markers [11]		X	X			X		C2 D16 or D17 [11]	X	X
Other Clinical Assessments										
Vital Signs	X	X	X	X	X	X	X	X	X	X
AEs/Con Meds and Treatments [13]	X	X	X	X	X	X	X	X	X	X
OMO-103 dosing [15]		X		X	X	X	X	X		

Footnotes for items [1]-[15] are listed in the protocol.

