4 STUDY VARIABLES AND COVARIATES

4.1 PRIMARY VARIABLES

The primary endpoints are as follows:

Part 1: Dose Escalation:

- Number of patients with a DLT;
- Number of patients with ≥ 1 related AE;
- Number of patients discontinuing study treatment due to related AEs.

The RP2D will be determined at the conclusion of Part 1.

Part 2: Dose Expansion

- Progression free survival (PFS) based on RECIST v1.1 as assessed by the Investigator.

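### The biopsy rule protects only a sole target lesion, so one of several RECIST target lesions may be biopsied before the first response scan and still be measured

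*Protocol*

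**What the plan says.** **Lesion choice.** The inclusion criteria for Parts 1 and 2 in the protocol synopsis expect tumour tissue at Screening and during treatment. The lesion to be biopsied must not have been irradiated and "should not be the only lesion being utilised as a measurable-disease target lesion for objective response assessment". A recent archival block can replace the Screening sample, in which case "a new biopsy does not need to be done at Screening".

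**Timing of the on-treatment biopsy.** The planned visits in the synopsis give "C1D16 or C1D17 (Day 16 or Day 17 for biopsy and only from dose level 3 onwards") for Part 1 and "C2D16 or C2D17 (Day 16 or Day 17 for biopsy") for Part 2. SAP section 3.1 gives the same days.

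**Timing of the scan.** The SAP flow charts (3.3.1 and 3.3.2) show CT/MRI at Screening and then in Cycle 3. Both cells carry footnote [8], and the biopsy cells carry footnote [9]. For these the SAP says only "Footnotes for items [1]-[15] are listed in the protocol".

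**Endpoints.** The protocol synopsis lists "ORR (primary efficacy endpoint"). SAP section 4.1 makes the Part 2 primary "Progression free survival (PFS) based on RECIST v1.1 as assessed by the Investigator". Both are RECIST endpoints.

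**Interim.** After 9 patients per group have had 3 cycles, recruitment could be stopped "If no response (as per RECIST v1.1) is seen during the interim analysis in at least one patient regardless of group". If a response is seen and there are no safety concerns, the study continues to 18 per group.

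**The concern.** The restriction covers one case only, a patient whose single target lesion would be biopsied. With two or more target lesions, one of them may be sampled and still be measured at the next scan. Tissue loss or scarring could make it look smaller. Bleeding or inflammation could make it look larger. Either would count in the sum of diameters as if it were a treatment effect, and could create or hide a response or a progression.

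The same sum feeds ORR, PFS, DCR, TTP, TTR, DOR and the waterfall plots, so the point stands whichever Part 2 primary endpoint applies. OS is not affected.

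The planned outputs would not reveal the problem. The PFS listing shell (Listing 16.2.7.1), which is repeated for the other efficacy parameters, shows subject, cohort, date and value, with nothing by lesion. SAP section 11.6 presents CT/MRI and biopsy data only if required. The same criteria already guard target lesions against one local intervention: a previously irradiated lesion counts only if it has since progressed. On-study biopsy of a target has no matching safeguard in the public text.

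**Working it through.** **Inputs.** From the documents: up to 24 patients in Part 1, 3 groups of 18 in Part 2, 9 per group at the interim, 3-week cycles (SAP section 3.1). Assumed, because the text does not print them: −30% for response and +20% for progression, both measured against baseline at the first scan, and target lesions of equal size.

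**The plan's own figures.** 24 + 3 × 18 = 78, the stated total. Interim: 3 × 9 = 27. No alpha, power or effect size is stated, so no power formula applies.

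**Order of events.** Day 1 of the next cycle is 21 days after Day 1 of the current one.
- Part 2: from C2D17 to C3D1 is 21 + 1 − 17 = 5 days. From C2D16 to the last day of Cycle 3 is 42 − 16 = 26 days.
- Part 1: from C1D17 to C3D1 is 42 + 1 − 17 = 26 days. From C1D16 to the last day of Cycle 3 is 63 − 16 = 47 days.

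So in both parts the biopsy precedes the first scheduled response scan, and in Part 2 by less than four weeks.

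**Change needed in the biopsied lesion.** With k equal targets, if the biopsied one changes by b and each of the others by o, the sum changes by [b + (k − 1)o]/k.
- Response from the biopsied lesion alone (o = 0): fall of 0.30k.
- Progression alone (o = 0): rise of 0.20k.
- Response when the others have truly fallen 20%: fall of 0.30k − 0.20(k − 1).
- Effect on the sum of a 20% change in the biopsied lesion: 20/k points.

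| Targets (k) | Fall for response, alone | Rise for progression, alone | Fall for response, others −20% | Shift in sum from a 20% change |
|---|---|---|---|---|
| 2 | 60% | 40% | 40% | 10 points |
| 3 | 90% | 60% | 50% | 6.7 points |
| 4 | 120% (impossible) | 80% | 60% | 5 points |
| 5 | 150% (impossible) | 100% | 70% | 4 points |

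If lesions are unequal, the fall needed alone is 30% divided by the biopsied lesion's share of the sum, so a dominant lesion needs less.

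**Effect on ORR.** One misclassified response is 1/18 = 5.6 points in a group, or 1/54 = 1.9 points over the three groups.

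**Effect on the interim.** If each of n exposed patients has chance q of a biopsy-caused response, the chance of at least one is 1 − (1 − q)^n. The documents give neither q nor n, so these rows show sensitivity only.

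| Exposed (n) | q | Chance of at least one |
|---|---|---|
| 27 | 0.25% | 6.5% |
| 27 | 0.5% | 12.7% |
| 27 | 1% | 23.8% |
| 27 | 2% | 42.0% |
| 14 | 0.1% | 1.4% |
| 14 | 1% | 13.1% |
| 5 | 0.5% | 2.5% |

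The range is too wide to say whether the risk at the interim is material. It shows only that a one-response condition is sensitive to a single misclassification.

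**The case against.** The strongest objection is that no mechanism is shown. The documents do not describe the biopsy technique, the amount of tissue taken or any effect on diameter. A reader might infer that the rule will produce false responses. The text does not support that: it supports only that a size change may enter the sum, in either direction. The table above also limits it, since a response from the biopsy alone needs near-removal of the lesion and few targets.

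Exposure is narrower than every patient. Tissue may come from any suitable primary or metastatic lesion, a biopsy may be judged not feasible after discussion with the sponsor, and sole targets are already barred. A Screening biopsy matters only if taken after the baseline scan. That order is not given, and an archival block may replace the sample.

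A reader might also infer that one false response carries an inactive drug to full enrolment. That is too strong. Without any response, recruitment only could be stopped, after discussion, so an inactive drug may continue anyway. What stands is that a false response removes the stated lack-of-activity trigger.

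A third tempting reading is that the plan has no rule for biopsied lesions. The public protocol text is mainly the synopsis. Footnotes [8] and [9], eligibility sections 10.2 and 10.3 (cited in SAP section 3.2) and the RECIST section (cited in SAP section 4.2) are not in it and may cover the point.

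Finally, an absolute ban on biopsying target lesions could cost paired tissue if the planned site became inaccessible. That objection stands, and the change proposed is not a ban.

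**Conclusion.** The gap in wording is real. One of several target lesions may be biopsied on treatment, before the first scheduled response scan, and nothing in the public text removes or flags it. Any resulting size change may enter every RECIST endpoint and the interim condition.

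The likely effect is small and its direction is unknown. Under the assumed thresholds and equal lesions, the realistic exposure is a patient with two or three targets who is already near a cut-off. Each response misclassified this way is worth 5.6 points of ORR in a group of 18. The interim probabilities rest on rates with no source and should not be read as estimates. Severity is minor. The change is worth making because it is cheap, not because bias has been demonstrated.

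**What to change.** First check flow-chart footnotes [8] and [9] and the full eligibility and RECIST sections of the protocol. If they do not already cover this:

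1. Add to the biopsy criterion that, where another measurable lesion is available, the lesion planned for biopsy is not selected as a target lesion.
2. Record which lesion was biopsied, when, and whether it is a target lesion.
3. Add to SAP section 11.3 a sensitivity analysis of ORR and PFS, also shown at the Part 2 interim, with any biopsied target lesion removed from the sum at baseline and at every later time point.

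**Cost.** No patient loses eligibility: under the present wording, anyone whose target lesion is biopsied already has at least one other target. The total stays at 78. The sum of diameters may rest on one lesion fewer, and there is a little more data capture and analysis. The change concerns which lesions are measured, not whether or when tissue is taken.

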1 INTRODUCTION

1.1 GENERAL

This statistical analysis plan (SAP) describes the statistical methods to be used during the reporting and analyses of data and should be read in conjunction with the study protocol and case report form (CRF).

This version of the plan has been developed using the current approved protocol amendment version Final v2.0 dated 18 November 2021 and annotated CRF version dated 19 July 2021. Any further changes to the protocol or CRF will be reviewed for potential impact on the SAP which will be amended if it is deemed necessary.

Draft versions of the SAP will undergo review by the Statistical Reviewer, Statistical Programmer, Project Manager, Medical Writer, Principal Investigator and the Sponsor representative. The analysis plan will be finalised and approved by the Sponsor prior to Database Lock (DBL).

1.2 CHANGES FROM PROTOCOL

Primary endpoint for part 2 will be Progression-Free Survival (PFS) instead of Objective Response Rate (ORR). The protocol stipulates 5 dose levels will be used. It was later established that more than 5 dose levels could be used if decided by the Safety Monitoring Committee (SMC).

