8 INTERIM ANALYSES

There will be an interim analysis performed at the end of Part 1.

In the dose expansion part, after half of the patients in all groups (i.e. 9 patients per group) have been included and treated for 3 cycles, efficacy and safety will be analysed. If no response (as per RECIST v1.1) is seen during the interim analysis for at least one patient regardless of group, or for safety reasons, recruitment could be stopped (or the dose reduced) following discussion between the Investigator, the SMC and the Sponsor.

If there are no safety concerns and a response is seen, the study will continue until 18 patients have been recruited in each group.

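### Protocol and SAP name different primary endpoints for Part 2 (ORR versus PFS), and the plan does not require the choice to be fixed before the Part 2 efficacy look

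*SAP*

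**What the plan says.** **Protocol.** The synopsis gives the Part 2 primary objective as "To assess the preliminary anti-tumour activity of OMO-103 monotherapy as measured by ORR according to standard criteria". Under efficacy parameters it lists "ORR (primary efficacy endpoint") and places PFS among the secondary endpoints.

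**SAP.** Section 1.1 says the plan was written against the "current approved protocol amendment version Final v2.0 dated 18 November 2021". Section 1.2 then declares a departure from it: "Primary endpoint for part 2 will be Progression-Free Survival (PFS) instead of Objective Response Rate (ORR"). Section 2 rewrites the Part 2 primary objective to match. Section 4.1 gives the primary variable as "Progression free survival (PFS) based on RECIST v1.1 as assessed by the Investigator". Section 11.3 names PFS as the primary efficacy endpoint and moves ORR to the secondary list. Section 1.3, on changes from previous SAP versions, mentions only the Part 1 interim analysis.

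**Timing.** SAP 1.1: "The analysis plan will be finalised and approved by the Sponsor prior to Database Lock (DBL"). SAP 8 plans an efficacy and safety analysis once 9 patients in each Part 2 group have had 3 cycles. Continuation to 18 per group is described thus: "If there are no safety concerns and a response is seen".

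**Analysis.** Section 11.3 treats all efficacy endpoints descriptively and promises Kaplan-Meier plots for time-to-event endpoints. Section 3.4 says the sample size has no formal statistical basis.

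**The concern.** Part 2 is the part of the study that asks whether the drug has anti-tumour activity, and its two governing documents give different answers to which measure decides that. A reader of the study report could not tell which result was the planned headline.

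Two features make this more than a clerical mismatch. First, the study is open label and unrandomised, progression is judged by the investigator, and efficacy is analysed halfway through Part 2. The SAP's only deadline, database lock, comes after all of that.

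Second, the substituted endpoint is harder to interpret here. Tumour shrinkage can largely be attributed to treatment without a control group. PFS in a single arm mixes drug effect with the natural pace of the disease, which differs across the three tumour types, and the plan gives no reference value to set it against.

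**Working it through.** **1. Figures in the plan.** There is no power, alpha, null response rate or reference median to reproduce. The sample size does reproduce: 24 + 3 × 18 = 78. The interim is at 18 / 2 = 9 per group, or 3 × 9 = 27 patients.

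**2. The documents side by side.**

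| Item | Protocol synopsis | SAP |
|---|---|---|
| Part 2 primary | ORR | PFS (1.2, 2, 4.1, 11.3) |
| PFS | Secondary | Primary |
| ORR | Primary | Secondary |
| Part 2 interim rule | RECIST response | RECIST response (8) |
| Reason and date of switch | – | None in the supplied text |

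**3. What could be known before the SAP must be final.** The interim looks for at least one response among 27 patients. The chance of seeing none is (1 − p)^27, where p is an assumed true ORR:

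- p = 2%: 0.98^27 = 0.58
- p = 5%: 0.95^27 = 0.25
- p = 10%: 0.90^27 = 0.058
- p = 20%: 0.80^27 = 0.002

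If the true ORR is low, a poor ORR result could well be visible while the primary endpoint may still be changed under SAP 1.1.

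**4. What 18 patients give on each endpoint.**

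- ORR, exact (Clopper-Pearson) 95% CI: 0/18 gives 0 to 18.5%; 2/18 (11.1%) gives 1.4 to 34.7%.
- Median PFS, assuming exponential times with d events, has limits of 2d / χ²(0.975; 2d) and 2d / χ²(0.025; 2d) times the estimate. For d = 18 these are 36 / 54.44 = 0.66 and 36 / 21.34 = 1.69. For d = 12 they are 24 / 39.36 = 0.61 and 24 / 12.40 = 1.94. An estimated median of 9 weeks with 18 events would carry an interval of about 6.0 to 15.2 weeks.

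Both endpoints are imprecise, so precision is not the case against PFS. The difficulty is that this interval has no control arm or stated benchmark to be compared with.

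**5. Effect of the scan schedule (conditional).** The Part 2 flow chart shows on-treatment CT/MRI at C3, and cycles last 3 weeks. The footnote giving the full schedule is in the protocol body, which was not supplied. *Assume* scans every 9 weeks, with progression recorded at the next scan. The observed median of 18 patients then equals 9 weeks whenever at least 10 progress by week 9. The probability that one patient does so is q = 1 − 2^(−9/m) for true median m:

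- m = 4.5 weeks: q = 0.75, P(at least 10 of 18) = 0.98
- m = 6 weeks: q = 0.646, P = 0.85
- m = 8 weeks: q = 0.541, P = 0.55

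On that assumption, quite different true medians would often be reported as the same 9 weeks. Step 4 treats event times as continuous and step 5 puts them on a grid, so the two are separate illustrations and should not be combined.

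**6. Whether the outputs fit the new endpoint.** The shell for Table 14.2.1.1 (PFS) has n, mean, SD, minimum, median and maximum, a layout that makes no allowance for censoring. The figure list in SAP 14.2 has Kaplan-Meier plots for TTP (14.2.6.1, 14.2.6.2) and TTR (14.2.7.1, 14.2.7.2) but none for PFS, despite the promise in 11.3. SAP 5 gives no PFS event or censoring rule; the protocol body may, but it is not available here.

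**The case against.** The switch is not concealed. It stands under the SAP's own heading for departures from protocol, and the table list in SAP 14.2 has both PFS and ORR in the Safety, Full Analysis and Per Protocol sets. Suppression of either result is therefore unlikely. That stands.

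A reader might infer that the endpoint was changed because response results were poor. The documents do not support this. The SAP's approval date is not in the supplied text, and database lock is an outer limit that does not show when this version was approved. SAP 1.3 does not list the switch as new in this version, which, if that section is complete, suggests it was already in an earlier one. A later protocol amendment adopting PFS cannot be excluded either.

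A reader might also put an error rate on choosing the better of two endpoints: at an assumed 10% each, 1 − 0.9² = 19% if they were independent. That has no footing here. Efficacy is descriptive, no success threshold exists, and both endpoints come from the same RECIST assessments.

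Preferring ORR is partly a design preference. The protocol itself treats prolonged absence of progression in Part 1 as grounds for adding tumour groups. Nor does a response-based interim contradict a PFS primary: the rule is non-binding, and response can be read after 3 cycles, when PFS is immature. These points rule out insisting on ORR. They do not remove the conflict between the documents, the missing reason and date, or the late deadline.

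**Conclusion.** The concern holds as a conflict between governing documents combined with a deadline that is too late. ORR is primary in the protocol and investigator-assessed PFS is primary in the SAP, with no reason or date visible. Finalisation is allowed after a 27-patient efficacy look in an open-label, uncontrolled study. The plan therefore leaves room for a choice informed by results; it is not shown that such a choice was made, or that any result is biased.

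If PFS stays primary, the planned outputs do not serve it: there is no reference value, the table shell is a mean and SD, and no Kaplan-Meier figure is listed. The 0.66 to 1.69 range for the median assumes exponential times and all 18 events observed. The results showing medians collapsing to 9 weeks hold only under the assumed 9-week scan schedule. The conflict itself rests on no assumption, since SAP 1.2 states it, and it should be settled before the Part 2 interim.

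**What to change.** 1. Make one primary endpoint stand in both documents. Either restore ORR in SAP 1.2, 2, 4.1 and 11.3 with PFS secondary, or amend the protocol to PFS, stating the date and reason of the change relative to the accrual and review of Part 2 data.
2. In SAP 1.1, require the primary endpoint and the SAP to be final before the Part 2 interim analysis, in place of database lock.
3. If PFS is kept:
   - replace the mean and SD shell (Tables 14.2.1.1 to 14.2.1.3, Part 2) with Kaplan-Meier estimates per tumour group, including the rate at a fixed scan time with its CI;
   - add a Kaplan-Meier PFS figure to the list in SAP 14.2;
   - report ORR with exact CIs per group alongside;
   - label PFS as descriptive because there is no control group.

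This takes SAP wording, revised shells and, on the second route, a short protocol amendment. It needs no new patients or data. The sponsor gives up the freedom to change the endpoint late.
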